causally to long-term outcomes, by reducing subsequent inflammation, immune suppression, and organ dysfunction [9]. Guidelines highlight the importance of early antibiotics and intravenous fluid resuscitation, but the delivery of early fluids is logistically challenging and its direct association with outcomes is uncertain [10]. The proposed primary/secondary clinical outcomes all directly reflect or impact on population health and wellbeing. Our focus is on early sepsis intervention, which has plausibility for modifying short and long-term outcomes. We chose not to study an exclusively ICU population, because, in this population, the intervention is later, selection bias is possible, and disease modification is less plausible. This trial will uniquely include all sepsis presenting to hospitals (>90% of sepsis patients in the NHS are managed in a general ward setting), for whom there is very limited research evidence around the timing and type or volume of intravenous fluid resuscitation. This initial study will establish whether a definitive study comparing 5% HAS with the current standard of balanced crystalloid fluid is feasible in this population and setting. If this study is feasible, it will inform the design and conduct of a larger definitive trial with results that will be generalisable to all patients with community acquired sepsis. The cost of sepsis is high, both during index admission and subsequent 'survivorship' [10]. The excess treatment costs for HAS are likely to be around £110/patient, substantially increasing current fluid costs, but HAS use has already increased 2-3 fold in many hospitals since 2012 consistent with data from outside the UK [6]. The potential economic gains (health/social) from effective early sepsis interventions are substantial and lifelong so our definitive study will include a health economic evaluation which will provide key information to guide HAS use in the NHS. For example, a reduction of 1 patient day in ICU would save around £1500 (equivalent to 12-13 units of HAS).

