#### **2.2.2 Secondary Endpoints**

[figure not shown]
1. In-hospital mortality and 90-day mortality;
2. Time to start of IMP;
3. Data completeness;
4. Study withdrawal;
5. Volume of randomised fluid delivered in each arm in the first 6hrs and 24hrs;
6. Proportion of participants needing critical care intervention: Intravenous vasopressors, renal replacement therapy and invasive ventilation;

7. Proportion of patients who receive any other fluid apart from intervention or control in first 6 hrs after recruitment;
8. Proportion of patients admitted to critical care (HDU/ICU); length of stay in critical care (HDU/ICU);
9. Length of hospital stay;
10. Proportion of patients readmitted in first 90 days after discharge;
11. Proportion of patients developing any of: acute kidney injury (Defined by NICE (<https://cks.nice.org.uk/acute-kidney-injury#!scenario>); pulmonary oedema (Radiology diagnosis or requirement for rescue management (new diuretic use); and allergy or anaphylaxis (Requirement for rescue management (antihistamines, adrenaline, intravenous fluids, steroids));
12. Health Related Quality of life (EQ-5D-5L) at 7 and 180 days for the first 50 patients;
13. Secondary care costs at 30 days (calculated from readmissions and length of stay at ward level and in critical care (HDU/ICU).

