
No formal cost-effectiveness analysis is planned, however, if data quality allows, an exploratory estimate of the incremental Quality Adjusted Life Years (QALYs) (at 180 days) and secondary care costs (at 30 days) will be made using the EQ-5D-5L. QALYs will be calculated by estimating a combined survival function and HRQoL function using the EQ-5D. Costs will be estimated by assigning national standard unit costs to inpatient stays (critical care and general ward level), readmissions and additional high costs activities observed in the study. Baseline (pre-admission) HQoL will be estimated using age/sex matched population reference data. In sensitivity analysis, surviving patients or proxies will be asked to provide a retrospective estimate of 1 month pre-admission modified EQ-5D-5L responses.

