Qualitative or health economic analysis will not be covered by this SAP. However, data from the statistics report may be used for health economics analyses.

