#### 4.6 Other analyses

The following data will be summarised descriptively, by randomised group and overall:

A	B	C
	Objective	Endpoints to display
1	Assess mortality rate during index hospitalisation, in-hospital and at 90 days	a) In-hospital mortality (index admission) and b) 90-day mortality
2	Assess the ability to deliver the trial including the time to first dose, data completeness and participant withdrawal	Data completeness (%)
3	Assess the total volume of intravenous fluid in each arm at 6 hours and 24 hours	Volume of randomised fluid delivered in each arm a) in the first 6hrs and b) more than 6hrs to 24hrs
4	Assess the level of critical care interventions administered	Proportion of participants needing critical care intervention: a) Intravenous vasopressors, b) renal replacement therapy and c) invasive ventilation
5	Investigate the length of hospital stay including critical care (HDU/ICU) admission	a) Proportion of patients admitted to critical care (HDU/ICU) b) Length of stay in critical care (HDU/ICU) c) Length of hospital stay
6	Investigate the proportion of patients readmitted to hospital in first 90 days after discharge	Proportion of patients readmitted in first 90 days after discharge

A	B	C
7	Delineate the proportion of patients developing any complications including acute kidney injury, pulmonary oedema and allergy including severe allergic reactions	Proportion of patients developing each, or any, of: a) acute kidney injury (as defined by NICE https://cks.nice.org.uk/acute-kidney-injury#!scenario ); b) pulmonary oedema (radiology diagnosis or requirement for rescue management (new diuretic use)); and c) allergy or anaphylaxis (requirement for rescue management (antihistamines, adrenaline, intravenous fluids, steroids))
For the economist		
8	To assess patient quality of life measures using EQ-5D-5L questionnaire	Health Related Quality of life (EQ-5D-5L) for the first 50 patients randomised (see section 4.8) a) at baseline b) at 7 days and c) at 180 days
9	To assess secondary care costs at 30 days	Service use at 30 days: a) number of readmissions, and b) length of stay at ward level and in critical care (HDU/ICU)

In addition, the following exploratory analyses will be considered. If deemed inappropriate based on available data, where feasible, suitable alternatives will be used:

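### As defined, the 30-day cost endpoint leaves out the trial fluid, and protocol section 10.2 does not clearly bring it back in

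*Protocol*

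**What the plan says.** Protocol section 2.2.2, item 13, defines the endpoint as "Secondary care costs at 30 days (calculated from readmissions and length of stay at ward level and in critical care (HDU/ICU"). The Trial Summary and the outcome table in section 8.1 carry the same definition. SAP section 4.6, row 9, gives the matching output: "Service use at 30 days: a) number of readmissions, and b) length of stay at ward level and in critical care (HDU/ICU").

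The costing method in protocol section 10.2, reproduced in SAP section 2, is wider: "Costs will be estimated by assigning national standard unit costs to inpatient stays (critical care and general ward level), readmissions and additional high costs activities" seen in the study. It does not say whether the trial fluid is one of those activities. The same paragraph sets the status of the work: "No formal cost-effectiveness analysis is planned, however, if data quality allows, an exploratory estimate" of QALYs and costs will be made. SAP section 3 adds: "Qualitative or health economic analysis will not be covered by this SAP".

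On price, protocol section 1.1 lists the cost of HAS among the reasons for the study (£106 against £2-4, a 25- to 50-fold difference) and says: "The excess treatment costs for HAS are likely to be around £110/patient, substantially increasing current fluid costs". Section 8.1 records that timing and volume of fluids are collected.

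**The concern.** The fluid is the one resource that allocation is designed to change, and its price is part of the protocol's argument for doing the study. The defined endpoint counts where HAS might save money (bed-days, readmissions) but not what HAS costs. With the same unit cost for a bed-day or readmission in both arms, those items cannot carry a price difference between the fluids.

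If the endpoint is applied as defined, the comparison of costs is shifted in one direction, towards HAS. The estimate is exploratory, but the study is meant to inform a definitive trial that will include a health economic evaluation. A pilot figure without the price of the intervention is a poor starting point for that.

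**Working it through.** **Inputs.** Protocol 1.1: HAS £106, crystalloid £2-4, excess around £110 per patient, one ICU day about £1,500, equated with 12-13 units of HAS. Protocol 4.1 and 5.5.1: 300 participants, 1:1, so about 150 receive HAS. Protocol 6.3: anticipated volumes in the first 3 hours of about 10 ml/kg (HAS) and 30 ml/kg (crystalloid).

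**1. The protocol's own figures.**
- Price ratio: 106/4 = 26.5 and 106/2 = 53, in line with the stated 25- to 50-fold.
- Excess per patient: 106 − 4 = £102 and 106 − 2 = £104. This is 5-7% below the stated £110, for which no derivation is shown.
- Unit price implied by the ICU comparison: 1,500/13 = £115 to 1,500/12 = £125. At £106 per unit, £1,500 would buy 1,500/106 = 14.2 units.

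The cost figures are of the same size but agree only roughly.

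**2. Effect of leaving the fluid out.** Let D be the HAS-minus-crystalloid difference in mean cost per patient.
- With fluid: D = D(stay and readmissions) + D(fluid).
- As item 13 is defined: D = D(stay and readmissions).
- Error: −D(fluid), about −£102 to −£110 per patient. Over 150 HAS patients: 150 × 102 = £15,300 to 150 × 110 = £16,500.

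If the fluid is costed under section 10.2, the error is £0.

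**3. Scale.** 110/1,500 = 0.07 ICU day per patient, or one ICU day per 1,500/110 = 13.6 patients. This is a break-even point only if ward days and readmissions are equal between arms.

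**4. If the prices are per container.** The protocol does not say whether £106 is per bottle or per patient. Assume 500 ml containers for both fluids, whole containers used, the anticipated 3-hour volumes, £106-125 per HAS bottle and £2-4 per crystalloid bag.

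| Weight | HAS | Crystalloid | Net excess |
|---|---|---|---|
| 50 kg | 500 ml, 1 bottle, £106-125 | 1,500 ml, 3 bags, £6-12 | 106 − 12 = £94 to 125 − 6 = £119 |
| 90 kg | 900 ml, 2 bottles, £212-250 | 2,700 ml, 6 bags, £12-24 | 212 − 24 = £188 to 250 − 12 = £238 |

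On this reading the omission is near £110 when one bottle is used and about twice that when two are used. Fluid given between 3 and 6 hours would add to both arms.

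**The case against.** **Section 10.2 may already cover it.** A reader might infer from item 13 that albumin is definitely excluded. The documents do not support that. Section 10.2 is the costing method, it is wider than the endpoint definition, and the protocol itself describes HAS as costly. This stands: the position is unclear, not settled. But activities is an odd word for a study fluid, and an item of about £106 is not obviously high-cost beside a £1,500 ICU day. If HAS was meant to be included, section 10.2 is at odds with the narrower definition in all three places where it appears.

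**The economist is not limited to row 9.** SAP section 3 lets health economists use data from the statistics report. That report will hold randomised fluid volumes (section 4.6, row 3) and crossover volumes (section 4.3). This also stands, and row 9 is not a costing specification. Having the volumes is still not an instruction to cost them.

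**Little depends on it.** The cost estimate is exploratory, EQ-5D-5L covers only the first 50 participants (about 25 per arm), and section 1.1 places the economic evaluation in the definitive trial. Sampling error may also be larger than the omission. As an illustration, assume 7.5% of patients enter critical care (middle of the 5-10% in section 1.1), with exponential stays of mean 2 to 6 days and £1,500 per day. The SD of critical-care days per patient is √(0.15 − 0.075²) = 0.38 times the mean stay. The standard error of the arm difference is then 0.38 × 2 × √(2/150) × 1,500, about £130, rising to about £395 at a mean of 6 days. So the omission would probably not decide any result here. It is systematic, however, and would not shrink in a larger trial that kept the same definition.

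**Readers can add £110 themselves.** They can, but that is a prior expectation, whereas the trial records the actual volumes.

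**Conclusion.** The point holds as a gap between the endpoint definition and the costing method. Item 13 and SAP row 9 omit the trial fluid, section 10.2 does not clearly include it, and no other text in either document says that it will be costed. If it is not costed, the HAS-minus-crystalloid difference is too low by roughly £102-110 per patient on the protocol's figures, and by more if £106 is a bottle price and more than one bottle is used. The direction favours HAS.

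Two stronger readings should be avoided. The first is that the trial will make HAS look £110 cheaper than it is. That requires the fluid to be excluded, which is not settled, and £110 is the protocol's approximate expectation, not a measured bias. The second is that one ICU day saved per 14 patients is the true break-even, which requires equal ward days and readmissions.

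The consequence is limited to an exploratory secondary output and does not touch recruitment or 30-day mortality. It is still worth correcting, because the rule as defined leaves out a cost that the protocol calls important, and the correction is cheap.

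**What to change.** 1. Reconcile item 13 (section 2.2.2, the Trial Summary and section 8.1) with section 10.2, so that all state that 30-day costs comprise trial fluid received (volume by type, crossover fluid included, times a stated unit price), readmissions, and days on the ward and in critical care.
2. Add volumes of HAS and of balanced crystalloid received to SAP section 4.6, row 9. Keep patients in their allocated arm and cost the fluid that they actually received.
3. Name the price source and the unit (per ml or per container opened), and show a range. Sections 6.1.7 and 6.2.7 let each pharmacy dispense any brand, the protocol gives no price per ml, and its own figures run from £106 to £125 per unit.
4. Report the arm difference with and without the fluid component.

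The SAP abstract describes recruitment in the past tense. The change may therefore be best made as a dated clarification in the SAP or a health economics plan, before costs by arm are seen.

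The cost is small. No new data are needed, since fluid volumes are already collected. A price source must be agreed, and the HAS arm's cost will look slightly less favourable.

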### **3. STUDY DESIGN**

This trial will be an open label two-arm, multicentre, pragmatic, parallel group randomised trial of adult patients with community acquired sepsis recruited from the Emergency Department and Medical and Surgical Assessment Units across ~15 UK NHS Hospitals. The treatment phase will be the first 6 hours following randomisation. 30-day and 90-day follow up will be conducted using routine data only. The exception to this will be the first 50 patients enrolled in the study, Health Related Quality of Life (HRQoL) will be measured using the EQ-5D-5L at baseline, 7 days and at 180 days. At baseline, the participant or their relative will be asked to recall the quality of life 4 weeks prior to the index hospital admission (modified EQ-5D-5L). Questionnaires will be administered by direct participant/relative completion or postal survey with telephone follow up for non-responders after two mailings two weeks apart.

### 3.1 Study Flowchart

## 4. STUDY POPULATION

### 4.1 NUMBER OF PARTICIPANTS

We aim to recruit 300 participants, from adults presenting to an Emergency Department or Medical/Surgical Assessment Units with signs or symptoms of community acquired sepsis and a NEWS (or NEWS2 if adopted by recruiting site) score of  $\geq 5$ . Recruitment will take place over approximately 12 months.

## **4.2 INCLUSION CRITERIA**

Adult patients (18 years or older) who present to UK NHS hospitals with community acquired sepsis meeting all of the 5 criteria:

1. Clinically suspected or proven infection resulting in principal reason for acute illness;
2. NEWS/NEWS2 score  $\geq 5$ ;
3. Hospital presentation within last 12hrs;
4. Clinician decision has been made that immediate (within 1 hour of assessment) intravenous fluid resuscitation is needed; and;
5. Ability to obtain informed consent.

## **4.3 EXCLUSION CRITERIA**

1.  $>1$  litre of intravenous crystalloid fluid or any intravenous HAS administered prior to eligibility assessment;
2. Clinically judged to require immediate surgery (within one hour of eligibility assessment);
3. Chronic renal replacement therapy;
4. Known allergy/adverse reaction to HAS;
5. Known contraindications to balanced crystalloid as per reference SmPC.
6. Known adverse reaction to blood products;
7. Palliation/end of life care (explicit decision by patient/family/carers in conjunction with clinical team that any active treatment beyond symptomatic relief is not appropriate);
8. Religious beliefs precluding HAS administration;
9. Previous recruitment in the trial;
10. Known recent severe traumatic brain injury (within 3 months);
11. Patients with permanent incapacity;
12. Known to have participated in interventional phase of another CTIMP study within the last 30 days.

## **4.4 CO-ENROLMENT**

### **4.4.1 Observational Studies**

Co-enrolment in observational studies will be permitted. For example, with studies that involve only the collection of data (e.g. questionnaires) or tissue samples (e.g. blood).

### **4.4.2 Interventional Phase CTIMP-CTIMP Co-enrolment**

Enrolling a participant in the interventional phase of more than one CTIMP (i.e. a participant receiving IMP(s) from more than one trial concurrently) is not permitted and participants will be excluded from the study if they have participated in another CTIMP within 30 days. This is to maintain participant safety, avoid drug interactions and to ensure there is appropriate levels of research burden.

### **4.4.3 CTIMP-CTIMP Co-enrolment**

In cases where participants are in long term follow-up (e.g. where follow data only is being collected) co-enrolment may be permitted. In such instances, the CTIMP-CTIMP Co-enrolment Checklist (POL008-F01) must be completed by the Sponsor

Representative(s) in conjunction with the CI prior to the co-enrolment proceeding. Where necessary, the combined risk assessment may need to be appraised as per ACCORD SOP GS002 (Combined Risk Assessment)

#### **4.4.4 CTIMP-Non-CTIMP Co-enrolment**

Participants who are active in the interventional phase of a non-CTIMP can be co-enrolled to a CTIMP provided the CTIMP-non-CTIMP Co-enrolment Checklist (POL008-F02) is completed by the Sponsor Representative(s) in conjunction with the CI prior to the co-enrolment proceeding. In addition, when considering permitting co-enrolment, investigators should be mindful of the potential burden upon participants, their families and research staff.

#### **4.4.5 Accidental/Unintentional Co-Enrolment Identified Retrospectively**

Investigators should aim to prevent accidental/unintentional co-enrolment by ensuring electronic and paper medical notes are checked for documentation of trial participation and by routinely asking participants if they are enrolled in another study prior to recruitment. The Sponsor's representatives require that incidents of accidental/unintentional co-enrolment be reported to the Sponsor as a protocol deviation/violation so they can determine the appropriate course of action.

## **5. PARTICIPANT SELECTION AND ENROLMENT**

### **5.1 IDENTIFYING PARTICIPANTS**

There will be no trial specific screening tests performed. The patient will receive routine acute clinical assessment including severity of illness assessment (vital signs and blood lactate measurement - which is needed to complete the randomisation) and be treated in accordance to current UK guidelines (Sepsis 6) [2,37]. The results of these will inform trial eligibility and the patient may be approached as soon as these are available. Patients may be approached up to 12 hours after presentation if their clinical condition means that fluid resuscitation needs to commence. This time window has been chosen as it allows the longest reasonable period for recruitment from arrival where the patient could be deemed to be receiving acute assessment.

Patient and clinician will be unaware of treatment allocation until after randomisation. The research team, where it is locally agreed that they are part of the clinical care team, will identify patients using triage information and clinical or electronic records in the Emergency Department, Medical or Surgical Assessment Units or any other area used for acute assessment in the recruiting site. In this case, it is anticipated they would identify patients and make the first approach. Any member of the clinical team who has received general and trial specific training and is on the delegation log may also identify patients in this way.

Where researchers are not considered to be part of the care team, the researcher should ask a member of the direct care team to identify suitable patients and ask permission from the patient to be approached by the researcher to discuss participation.

### **5.1.2 Pregnant Participants**

Pregnancy is not an exclusion criteria as the interventions are thought to be safe for use during pregnancy according to their representative Summary of Product Characteristics (SPC). The safety of Human Albumin Solution for use in human pregnancy has not been established in controlled clinical trials. However, clinical experience with albumin suggests that no harmful effects on the course of pregnancy, or on the foetus and the neonate are to be expected. Human Albumin is also a normal constituent of human blood. Compound Sodium Lactate solution can be used safely during pregnancy and lactation as long as the electrolyte and fluid balance is controlled.

## **5.2 CONSENTING PARTICIPANTS**

The consent pathway below will be followed to determine the appropriate mechanism of consent to use for an individual participant and details where consent to continue is needed.

### **5.2.1. Patient consent**

Potentially eligible participants who are willing to take part in the study, and have capacity to do so, will be asked to provide written informed consent. Consent will be obtained by trained members of the clinical team or members of the research team who have been delegated this responsibility. The Investigator is responsible for the delivery of processes to ensure informed consent is obtained before any protocol specific procedures are carried out. The decision of a patient to participate in clinical research is voluntary and should be based on a clear understanding of what is involved.

The patient will be given a Patient Information Sheet (PIS), which will explain the aims of the trial and the potential risks and benefits of the study treatments. If necessary, a Summary PIS will be provided first to provide a brief outline of the study and allow potential participants to decide whether or not they wish to proceed and before the full Patient Information Sheet is provided.

The patient will be given enough time to consider the trial and ask questions regarding their participation in the trial. Due to the need to start treatment within one hour, there may not be long for the participant to consider the trial. Ideally, a period of 30-40 minutes will be given but it may be only 10-15 minutes due to the need for fluid resuscitation to begin. The research teams are experienced at recruiting patients in the emergency environment and given the nature of the intervention and the burden of the trial we believe this to be reasonable. Potential participants will receive adequate oral and written information. The oral explanation to the patient will be performed by a member of the research team or a trained and delegated member of the clinical team and must cover all the elements specified in the Participant Information Sheet and Consent Form. The patient must be given every opportunity to clarify any points they do not understand and, if necessary, ask for more information. The patient must be given sufficient time to consider all the information provided. It should be emphasised that the patient may withdraw their consent to participate at any time without loss of

benefits to which they otherwise would be entitled. The participant will be informed and agree to their medical records being inspected by representatives of the sponsor(s). The Investigator or delegated member of the trial team and the participant will sign and date the Consent Form to confirm that consent has been obtained. If the participant is unable to sign the consent form for themselves then the witnessed verbal consent form can be used and written consent does not need to be obtained in addition to this. The original consent form will be filed in the Investigator Site File (ISF), the participant will receive a copy of this document and a copy filed in the participant's medical notes.

Capacity will be assessed by the Principal Investigator (PI) or a clinician responsible for the treatment of the participant. This assessment of capacity will be documented in the participant's medical records.

